8.2.2 Adverse events summaries

TEAEs will be summarized by the most recent dose level prior to onset of TEAEs for entire study analysis or the highest dose within a cycle for by-cycle analysis and RLZ total including the number and percentage of study participants and frequency. Additional details are described below:

1. Overview of TEAEs by entire study and study cycle will include following categories: any TEAEs, serious TEAEs, participant discontinuation due to TEAEs, permanent withdrawal of IMP due to TEAEs, temporary withdrawal of IMP due to TEAEs, TEAEs requiring dose change, treatment-related TEAEs, severe TEAEs, TEAEs leading to death, all deaths (AEs leading to death). Additionally, summary of TEAEs by study cycle, fixed dose and weight subgroups will be conducted as specified in [Section 4.9.2](#).
2. Incidence of TEAEs will be summarized for entire study by SOC, HLT, PT for:
 - Any TEAEs
 - Any TEAEs during Treatment Period
 - Any TEAEs by maximum intensity (mild, moderate and severe)
 - Any TEAEs by relationship
 - Severe TEAEs

- Non-serious TEAEs above reporting threshold of 5% of study participants
- Fatal TEAEs
- Fatal TEAEs by relationship
- Serious TEAEs
- Serious TEAEs by relationship
- Participant discontinuation due to TEAEs
- TEAEs leading to permanent withdrawal of IMP
- TEAEs leading to temporary withdrawal of IMP
- TEAEs requiring dose change
- Treatment-emergent AESM
- Treatment-emergent AESI

3. Incidence of any TEAEs by entire study and study cycle will be summarized by decreasing participant count of PT in RLZ total. Same analysis will be repeated by fixed dose and weight subgroups as specified in [Section 4.9.2](#).

4. Incidence of TEAEs will also be summarized by SOC, HLT, PT, and the highest dose level prior to onset of TEAEs and RLZ total for each study cycle, including the number and percentage of study participants and frequency for:

- Any TEAEs
- Severe TEAEs
- Serious TEAEs
- Participant discontinuation due to TEAEs
- TEAEs leading to permanent withdrawal of IMP

5. Overview of non-TEAEs by entire study will include following categories: any non-TEAEs, serious non-TEAEs, participant discontinuation due to non-TEAEs, permanent withdrawal of IMP due to non-TEAEs, temporary withdrawal of IMP due to non-TEAEs, severe non-TEAEs, non-TEAEs leading to death.

6. Incidence of non-TEAEs will be summarized for entire study by SOC, HLT, PT for:

- Any non-TEAEs
- Severe non-TEAEs
- Serious non-TEAEs
- Fatal non-TEAEs
- Incidence of Non-TEAEs leading to discontinuations

AESMs include severe and/or serious headache and suspected aseptic meningitis.

AESIs are the cases of potential Hy's Law (see [Section 8.3.1](#)).

AESMs and AESIs will be identified based on the assessment by the Investigator as recorded in the CRF. An AE will be counted as an AESM if there is a 'yes' response to the question "Adverse event of Special Monitoring?" and 'no' otherwise. An AE will be counted as an AESI if there is a 'yes' response to the question "Adverse Event of Special Interest?" and 'no' otherwise.

When applicable adverse event summaries will be ordered by alphabetical SOC, alphabetical HLT within SOC and decreasing frequency of PT in the RLZ total column for tables.

Listings of all TEAEs, all non-serious TEAEs, serious TEAEs, permanent withdrawal of IMP due to TEAEs, study participant discontinuation from study due to TEAEs, AEs leading to death, AESIs, AESMs, intermittent period AEs, persistent AEs, non TEAEs and TEAEs for participants who used manual push will be presented by treatment group, study cycle and participant. Most recent dose will be presented in listing even when the AE start date is partial. A flag will be added in those listings to highlight whether the AE occurred on manual push or not.

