1.3 Schedule of activities, Table 1-2, Table 1-3	New footnotes "k" (Table 1-2) and "h" (Table 1-3): Added to clarify that a full neurological examination should be performed in the event of severe and/or serious headache or suspected aseptic meningitis. Subsequent footnotes have been reordered.	The accumulated safety data on rozanolixizumab led to an update of the adverse events requiring special monitoring. As of the cut-off date of the IB (13 Jul 2022), the following serious adverse events (SAEs) Headache and Meningitis

Section # and Name	Description of Change	Brief Rationale
1.3 Schedule of activities, Table 1-2, Table 1-3 8.9 Biomarkers	Footnote q (now r, Table 1-2), footnote m (now n, Table 1-3), and text (Section 8.9): Updated to remove the former AESM of severe GI disorders, to add the new AESM of suspected aseptic meningitis, and to further detail the sampling time.	Aseptic (PT terms) suggest a possible causal relationship to rozanolixizumab; based on both their temporal association with investigational medicinal product (IMP) infusion (primarily initial infusion) and given the events have occurred more than once in the rozanolixizumab clinical development program.
1.3.1 Additional study assessments	New section added to detail additional study assessments in case of AESM of severe and/or serious headache or the new AESM of suspected aseptic meningitis.	
2.3 Benefit/Risk assessment	Revised text on most common adverse drug reactions, safety concerns, and other safety topics of interest.	
8.3.7 Adverse events of special monitoring	The AESM have been updated to delete severe GI disorders and opportunistic infections and to add suspected aseptic meningitis.	
10.2 Appendix 2: Clinical Laboratory Tests, Table 10-1	Added cross-reference to Table 1-6 for additional assessments that may be required in case of AESM.	
1.1 Synopsis, Objectives and endpoints 3 Objectives and endpoints	The other endpoint specific to Change from Baseline (Day 1) in [REDACTED] [REDACTED] [REDACTED] has been updated to delete “AESM of severe headache”.	The sampling of complement for severe headache was removed to align with a new guidance on biomarker collection.
1.3 Schedule of activities, Table 1-2, Table 1-3 8.9.1 Immunological assessments 9.4.2.3 Immunological analyses	Footnote s (now t, Table 1-2), footnote n (now o, Table 1-3), and text (Section 8.9.1 and Section 9.4.2.3): Updated to delete “severe headache”.	

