1 INTRODUCTION

The purpose of this statistical analysis plan (SAP) is to provide all information that is necessary to perform the statistical analyses of study MG0007, including three interim cuts and final analysis. It also defines the summary tables, figures and listings (TFLs) to be included in the final Clinical Study Report (CSR) according to the protocol.

This SAP is based upon, and assumes familiarity with, the following documents:

- Protocol Amendment 3: 03 Oct 2022
- Rozanolixizumab Program Safety Analysis Plan: 16 Nov 2023

If a future protocol amendment necessitates a substantial change to the statistical analysis of the study data, this SAP may be amended accordingly. Changes to the analysis from the protocol are documented in [Section 3.9](#). The content of this SAP is compatible with the International Council for Harmonisation (ICH)/Food and Drug Administration (FDA) E9 Guidance documents.

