2.2.1.2 Other safety endpoints

- Occurrence of serious TEAEs
- Occurrence of treatment-emergent adverse events of special monitoring (AESM)
- Vital sign values and changes from Baseline (Day 1) (systolic and diastolic blood pressure [BP] and pulse rate at each scheduled assessment during Treatment and Observation Periods)
- 12-lead electrocardiogram (ECG) values and change from Baseline at each scheduled assessment during the Treatment and Observation Periods
- Laboratory values and changes from Baseline at each scheduled assessment during the Treatment and Observation Periods (hematology, clinical chemistry, and urinalysis)

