4.4 Interim analyses and data monitoring

Submission Cut and Day 120 cut will be conducted during the study. For Submission Cut, all the analyses specified in the SAP will be performed using all the data of all participants till 08 July 2022 for submission purposes. For Day 120 cut, only selected analyses of safety in the SAP will be performed using all the data till 07 October 2022.

An overarching Rozanolixizumab program IDMC (pIDMC) will oversee the safety of this study by reviewing safety data at periodic timepoints with other Rozanolixizumab studies. The scope and role of the overarching pIDMC will be described in overarching IDMC charter and its study specific attachment.

Data requirements for each interim cut are summarized below:

- Submission Cut: PK, NAb, and ADA are required. PK and ADA data will be transferred to PXL 7 weeks after the MG0003 database lock. Bioanalysis of PK and ADA samples takes around 10 weeks. In order to meet the timelines for the PK/ADA data transfer to PXL, PK and ADA samples will need to be sent to the LGC lab around 10 weeks before the data transfer.
- Day 120 cut: PK, NAb, and ADA are required. Available samples transferred to Lab around 10 weeks before data transfer, data transfer around 1.5 weeks before the review.

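### The entire-study AESM table counts CRF ticks with no rule for the change of AESM list at Protocol Amendment 3, so it can pool two definitions

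*SAP*

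**What the plan says.** SAP 8.2.2 gives both a definition and a counting rule. The definition is "AESMs include severe and/or serious headache and suspected aseptic meningitis". The rule is that "AESMs and AESIs will be identified based on the assessment by the Investigator as recorded in the CRF", and in detail that "An AE will be counted as an AESM if there is a" 'yes' answer to the special-monitoring question on the form. Any other answer means the event is not an AESM. Treatment-emergent AESMs are tabulated once, for the entire study, by SOC, HLT and PT, and AESMs are also listed.

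The list behind the tick changed during the study. The protocol's summary of changes for Amendment 3 records, for Section 8.3.7: "The AESM have been updated to delete severe GI disorders and opportunistic infections and to add suspected aseptic meningitis". The SAP introduction dates that version: "Protocol Amendment 3: 03 Oct 2022".

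SAP 4.4 shows that data collection was under way by then. The Submission Cut runs all SAP analyses "using all the data of all participants till 08 July 2022 for submission purposes". For the Day 120 cut, "only selected analyses of safety in the SAP will be performed using all the data till 07 October 2022".

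SAP 13.7 defines adverse events of focus (AEOF) by MedDRA terms. Its notes mark possible aseptic meningitis as also an AESM. They mark opportunistic infections the same way, although SAP 8.2.2 and Protocol 8.3.7 no longer list them.

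**The concern.** The tick records what the investigator judged against the list in force at the time. The SAP defines AESM by the current list but counts every tick, whenever it was made. The two agree only if ticks were harmonised after Amendment 3, and the SAP does not ask for that.

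Occurrence of treatment-emergent AESM is a stated safety endpoint (SAP 2.2.1.2). The amendment's rationale cites serious headache and aseptic meningitis events in the rozanolixizumab programme. An aseptic meningitis count whose completeness depends on calendar time is therefore a weak point where readers will look closely. A count that also holds off-list events does not estimate what the SAP says it estimates.

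**Working it through.** The study is descriptive, with no power or alpha figure on this point to reproduce. The check is a comparison of texts, date arithmetic, and an illustration on assumed inputs. The amendment log is used only to show that the collected definition changed, not as a contradiction with current text.

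**1. Dates.**
- Submission Cut to Amendment 3: 08 Jul to 03 Oct 2022 = 23 + 31 + 30 + 3 = 87 days. Ticks made by that cut precede the change.
- Amendment 3 to Day 120 cut: 03 to 07 Oct 2022 = 4 days.
- Amendment 3 to SAP Amendment 2, which updated the AESM definition: 03 Oct 2022 to 22 Feb 2024 = 365 + 142 = 507 days.
- Protocol 10.1.1 requires ethics approval before changes are made, apart from immediate hazards. The switch at sites need not fall on 03 Oct 2022.

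The final entire-study table therefore spans both lists.

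**2. Rule against definition.**

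| Event | In the SAP 8.2.2 definition? | Listed before Amendment 3? | Result of the tick rule |
|---|---|---|---|
| Severe GI disorder, ticked before the change | No | Yes | Counted |
| Opportunistic infection, ticked before the change | No (SAP 13.7 note says yes) | Yes | Counted |
| Suspected aseptic meningitis before the change, not ticked | Yes | No | Not counted |
| Suspected aseptic meningitis after the change, ticked | Yes | – | Counted |

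No SAP sentence restricts ticks to the current list, asks for earlier events to be re-flagged, or splits the table by amendment. The SAP does handle a comparable change elsewhere: SAP 10.2.2 sets rules for anti-AChR results from two reagents.

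**3. What the AEOF tables recover.** SAP 8.2.3 tabulates AEOF for the entire study regardless of the tick, with separate serious and severe tables. Aseptic meningitis is selected by the narrow search of SMQ 'Noninfectious meningitis'. Headache is every event in HLT 'Headaches'. If *A* participants have a severe headache and *B* a serious one, the number with either lies between max(*A*, *B*) and *A* + *B*. The tables do not fix it further, so no AEOF table gives the AESM count.

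**4. Illustration of the possible omission (assumed inputs).** Let *f* be the share of true aseptic meningitis events before the change and *q* the share of those ticked, at the time or later. Expected share captured = 1 − *f*(1 − *q*).

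| *f* | *q* = 0 | *q* = 0.5 | *q* = 1 |
|---|---|---|---|
| 0.25 | 75% | 87.5% | 100% |
| 0.50 | 50% | 75% | 100% |
| 0.75 | 25% | 62.5% | 100% |

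With two true events and *q* = 0, the chance of missing at least one is 1 − (1 − *f*)² = 0.44, 0.75 and 0.94. The documents supply neither *f* nor *q*. The table shows what the count depends on and does not estimate a loss.

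**The case against.** The best defence is that little is hidden. Coded aseptic meningitis appears in the AEOF tables whatever was ticked. Severe headaches and serious headaches are each tabulated. An off-list tick would show under its own preferred term in the AESM table and listing. AESM is not a primary endpoint, and no decision rule uses the count. All of this stands and limits the consequence. It does not supply the AESM count or make the counting rule match the definition.

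Two stronger readings are tempting, and the documents support neither.

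- A reader might infer that earlier aseptic meningitis events were missed and the signal understated. The programme-level reports in the amendment rationale do not show that any such event occurred in MG0007 before the change. The form's question was generic, so a tick was not shown to be impossible, and an early case might have been ticked as severe headache. CRF entries can be corrected, and the documents do not say whether earlier events were re-flagged.
- A reader might infer that the Submission Cut itself mixed two lists. It precedes Amendment 3, so ticks made by then fall under one list. It proves only that data precede the change.

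A third objection concerns the remedy. Protocol 8.3.7 and Appendix 14 require reporting on suspicion, before the workup is complete. A suspected case later given another diagnosis is still an AESM but may fall outside a narrow SMQ. Replacing the tick entirely could lose such cases, so ticks should be kept and reconciled.

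**Conclusion.** The concern holds in a limited form. Followed as written, SAP 8.2.2 lets one entire-study table pool ticks made under two AESM lists. The table can include severe GI disorders and opportunistic infections that the SAP's definition excludes, and it may omit aseptic meningitis that was not ticked before the change. The label on opportunistic infections in SAP 13.7 contradicts 8.2.2 whatever sites did.

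The size cannot be computed. It depends on event counts, CRF revision dates and any re-flagging, none of which is given. The conclusion assumes that sites ticked against the list in force, and that no harmonisation was done outside these documents. If ticks were fully reconciled to the current list, the counts would be right and only the SAP text would need correcting.

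The change should be made because a stated endpoint is affected and the remedy is cheap.

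**What to change.** In SAP 8.2.2, state that the current list applies to all events regardless of onset date, and derive one AESM flag from:

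- events in HLT 'Headaches' that are severe (intensity as mapped in SAP 8.2.1) or serious;
- events in SMQ 'Noninfectious meningitis', narrow search;
- events the investigator ticked as suspected aseptic meningitis, identified from the reported term, even when the final coded term falls outside that search.

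Leave ticks for events outside the current list out of the main count and show them separately. Reconcile the derived flag against the tick and list the differences. An acceptable alternative is to present AESMs before and after Amendment 3, using each site's implementation date if it is available. In SAP 13.7, delete the note that opportunistic infections are in AESM.

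The cost is a few lines of text, one derived flag and a small difference from earlier tick-based counts. One limit remains: a suspected case before the change that was neither ticked nor coded within the SMQ would be found only by a site query.

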8.2.3 Adverse events of focus

Rozanolixizumab adverse events of focus (AEOF) include the following categories:

- Headaches
- Aseptic meningitis
- Gastrointestinal disturbances
- Hypersensitivity reactions
- Anaphylactic reactions
- Injection site reaction
- Infections
- Opportunistic infections
- Reductions in albumin and plasma proteins
- Effects on the kidney
- Drug related hepatic disorders
- Effects on lipids

1. The number and percentage of study participants who experience each category of the AEOF will be summarized by most recent dose level prior to onset of the AEOF and RLZ total treatment group. The following summaries will be presented for entire study by SOC, HLT, and PT:

- Treatment-emergent AEOF
- Serious Treatment-emergent AEOF
- Treatment-emergent AEOF by maximum intensity (mild, moderate and severe)

- Treatment-emergent AEOF hypersensitivity reactions, anaphylactic reactions and injection site reactions by ADA
- Severe Treatment-emergent AEOF

2. Incidence of TEAEs will also be summarized by SOC, HLT, PT, and the highest dose level prior to onset of TEAEs and RLZ total for each study cycle, including the number and percentage of study participants and frequency for:

- Treatment-emergent AEOF
- Severe Treatment-emergent AEOF

3. Graphs for AEOF headache in Treatment Period by time of onset (relative to infusion and cycle), severity, causality and duration for each study participant will also be provided. A graph for AEOF headache by participant for participants with at least two headaches in this study will also be provided.

A by-subject listing of all AEOF by category (as listed above) will be provided by treatment group, study cycle and participant. Most recent dose will be presented in listing even when the AE start date is partial. Further details related to the statistical analysis of the above mentioned treatment-emergent AEOFs are provided in [Section 13.7](#).

8.3 Clinical laboratory evaluations

The following table ([Table 8-1](#)) lists safety laboratory assessments that are collected throughout the study:

Table 8-1: Clinical Laboratory Parameters

Laboratory Assessments	Parameters			
Hematology	Platelet Count	RBC Indices: Mean corpuscular volume Mean corpuscular hemoglobin %Reticulocytes	White Blood Cell (WBC) Count with Absolute Count and Differential: Neutrophils Lymphocytes Monocytes Eosinophils Basophils	
	Red Blood Cell (RBC) Count			
	Hemoglobin			
	Hematocrit			
Clinical Chemistry ^a	Blood Urea Nitrogen (BUN)	Potassium	Aspartate Aminotransferase (AST) / Serum Glutamic-Oxaloacetic	Total and direct bilirubin

Table 8-1: Clinical Laboratory Parameters

Laboratory Assessments	Parameters			
			Transaminase (SGOT)	
	Creatinine	Sodium	Alanine Aminotransferase (ALT)/ Serum Glutamic-Pyruvic Transaminase (SGPT)	Total Protein Albumin
	Glucose (fasting state, preferred)	Calcium	Alkaline phosphatase	C-reactive protein (CRP)
	Lactate dehydrogenase (LDH)	Triglycerides	Low-density lipoprotein (LDL) High-density lipoprotein (HDL)	Total Cholesterol
Routine Urinalysis	
 Specific gravity pH, glucose, protein, ketones, albumin, bilirubin, urobilinogen, nitrite, leukocyte esterase, hemoglobin by dipstick, albumin/creatinine ratio, creatinine Microscopic examination (if blood or protein is abnormal) 			
Other Screening Tests	
 Follicle-stimulating hormone and estradiol (as needed in women of non-childbearing potential only) Urine drug screen (to include at minimum: amphetamines, barbiturates, cocaine, opiates, cannabinoids and benzodiazepines) Serum or urine human chorionic gonadotropin pregnancy test (as needed for women of childbearing potential)^b PTT and INR Serology testing (for Hepatitis B, Hepatitis C, and HIV) All study-required laboratory assessments will be performed by a central laboratory. 
The results of each test must be entered into the eCRF.
			

NOTES:
 
For additional assessments that may be required in case of AESM, see protocol Table 1-6.
 
^a Details of liver chemistry stopping criteria and required actions and follow-up assessments after liver stopping or monitoring event are given in protocol Section 7.1.1 and Appendix 6 (Section 13.6). PDILI criteria are given in the SAP Section 8.3.1.
				

Table 8–1: Clinical Laboratory Parameters

Laboratory Assessments	Parameters
^b Local urine testing will be standard for the protocol unless serum testing is required by local regulation or Institutional Review Board (IRB)/Independent Ethics Committee (IEC).	

Chemistry, hematology and quantitative urinalysis (observed value, absolute change from Baseline) will be summarized in standard unit using descriptive statistics for each study cycle by actual dose received within the study cycle at each scheduled visit and RLZ total.

The central lab data will be used for the summary tables. Repeated lab measurements will be handled per [Section 4.3](#).

Measurements below the lower limit of quantification (BLQ) will be imputed with half of the lower limit of quantification (LLOQ), and measurements above the upper limit of quantification (ALQ) will be imputed to the upper quantification limit for the purpose of quantitative summaries.

An assessment is markedly abnormal (MA) if it meets the MA criteria outlined in [Section 13.6](#).

A **treatment-emergent (TE)** assessment is defined as any assessment that was not present prior to the first administration of rozanolixizumab of each treatment cycle or 8 weeks (56 days) after the last dose of each treatment cycle. **TE period** for each cycle is from first administration of rozanolixizumab and 8 weeks (56 days) after last dose of rozanolixizuman of each cycle.

The following rules will be used to assign a TE assessment to a study period in each study cycle:

Treatment Period: a TE assessment will be assigned to the Treatment Period for the tabulations if the start date of the assessment is on or after the date of the first administration of MG0007 IMP on Day 1, up to 7 days after the last dose of IMP in each cycle;

Observation Period: a TE assessment will be assigned to the Observation Period for the tabulations if the start date of the assessment is greater than the day after Treatment Period until 8 weeks (56 days) following the final dose in each study cycle;

An **intermittent period** assessment is defined as any assessment occurring after the 8-week (56-day) TE period, prior to the next cycle.

The number and percentage of participants who have TE MA chemistry and hematology assessment will be summarized for entire study by initial dose level and RLZ total, and for each study cycle by actual dose received within the study cycle and RLZ total at any visit (including unscheduled visit). The number and percentage of participants who have MA chemistry and hematology assessment during Intermittent Period will also be summarized for entire study by initial dose level and RLZ total, and for each study cycle by actual dose received within the study cycle and RLZ total at any visit (including unscheduled visit).

The laboratory variables that are categorized as normal, high or low based on the reference range supplied by the analytical laboratory will be presented in shift tables from Baseline to any post-Baseline visit (including unscheduled visit) for entire study by RLZ total only, and for each study cycle by actual dose received within the study cycle and RLZ total. All laboratory test results

will be listed, including Baseline, scheduled and unscheduled visits with results in standard unit. Values outside the reference range for the continuous variables will be flagged in the listings. The reference ranges will also be reported in the listings.

Mean values in albumin, C-reactive protein, White Blood Cell Count with absolute count and differential (neutrophils, lymphocytes, monocytes, eosinophils and basophils) and platelets will be plotted over time by study cycle and actual dose level received within study cycle and RLZ total with all treatments overlaid on the same plot.

In addition, the listings will include a flag for values identified as MA. Additional lab test, including pregnancy testing, will also be listed.

